5 STUDY ACTIVITIES

5.1 Eligibility Criteria

Subjects must meet all of the following criteria to be included in the study. Anything other than a positive response to the questions below will result in exclusion from the study.

Consent

- 1. Parent or legal guardian has voluntarily signed and dated an informed consent form, approved by an institutional review board (IRB), after the nature of the study has been explained and the subject and the subject's parent or legal guardian has had the opportunity to ask questions. The informed consent must be signed before any study-specific procedures are performed or before any concomitant medication is discontinued for the purpose of the study. Pediatric subjects will be included in all discussions in order to obtain verbal and/or written assent.

Disease Activity

- 2. Children with a diagnosis of CPP, either treatment-naïve or previously treated with a GnRHa.
- 3. Chronological age at the appearance of pubertal changes < 8 years in females and < 9 years in males at Day 1 of the study.

Demographic and Laboratory Assessments

- 4. Bone age advancement over chronological age at least 1 year at time of CPP diagnosis or first GnRHa therapy.
- 5. Bone age < 13 years for females and < 14 years for males.
- 6. In general good health with no uncontrolled, clinically significant disease that could interfere with bone maturation or mask the objectives of this protocol as assessed by the investigator.
- 7. No abnormal laboratory value that suggests a clinically significant underlying disease or condition that may prevent the subject from entering the study.
- 8. Willing and able to comply with procedures required in this protocol.
- 9. No diagnosis of short stature, i.e., more than 2.25 SD below the mean height for age (growth chart assessment).

Subject History

- 10. No diagnosis of incomplete precocious puberty, peripheral precocious puberty; evidence of any abnormal pituitary, hypothalamic, adrenal, thyroid, and gonadal function other than premature secretion of gonadotropins not adequately controlled; no unstable intracranial tumors (unresponsive to treatment/expanding) except hamartoma.

- 11. No concomitant medical condition that, in the opinion of the investigator, may expose a subject to an unacceptable level of safety risk or that affects subject compliance.
- 12. No history of clinically significant medical conditions or any other reason that the investigator determines would **interfere with the subject's participation** in this study or would make the subject an unsuitable candidate to receive study drug.
- 13. No history of an **allergic reaction** or significant sensitivity to constituents of the study drug (and its excipients) and/or other products in the same class.

Pregnancy

- 14. A **negative serum pregnancy test** for female subjects \geq 10 years of age at Screening and negative urine pregnancy test on Day 1 prior to study drug administration. For female subjects $<$ 10 years of age, pregnancy tests may be performed at Screening and on Day 1 at the discretion of the principal investigator.

Concomitant Medications

- 15. Must have discontinued therapy with medroxyprogesterone acetate, growth hormone, insulin-like growth factor-1 (IGF-1), or estrogen or testosterone preparations at least 5 half-lives or 4 weeks prior to Screening, whichever is longer.
- 16. Must not have been treated with **any investigational drug** within 30 days or 5 half-lives of the drug (whichever is longer) prior to Screening or is currently enrolled in another clinical study.

Additional Criteria for Subjects Naïve to GnRHa treatment

- 17. Females 2 – 8 years of age, inclusive, or males 2 – 9 years, inclusive, on Day 1.
- 18. Pretreatment pubertal response to GnRHa stimulation test ($LH \geq 6$ mIU/mL) at Screening.
- 19. Breast pubertal staging (modified Tanner) of at least 2 in females; testicular volume of at least 4 cc in males at Screening.

Additional Criteria for Subjects Previously Treated with a GnRHa

- 20. Females 2 – 10 years of age, inclusive, or males 2 – 11 years of age, inclusive, on Day 1.
- 21. Must have been on GnRHa therapy for at least 6 months prior to Day 1.
- 22. Should have documented maintenance of LH suppression as evidenced by peak stimulated $LH < 4$ mIU/mL at Screening.

5.2 Prohibited Medications and Therapy

All other investigational drugs are prohibited during the study.

Any medications with a known positive or negative effect on either growth or the assessment of sex steroids will not be permitted for use during the study. Examples are as follows:

- GnRH agonists other than study drug*
- GnRH antagonists
- High dose corticosteroids (e.g., doses greater than hydrocortisone 5 mg/m² body surface area/day)
- Growth hormone
- IGF-1
- Testosterone
- Estrogen

*The GnRH agonist required to perform the stimulation test is allowed during the study (see Operations Manual Section 3.15).

5.3 Prior and Concomitant Therapy

Any medication or vaccine (including over-the-counter or prescription medicines, vitamins, and/or herbal supplements) that the subject is receiving within 30 days prior to Screening, at the time of enrollment, and during the study must be recorded through the 12-week follow-up phone call.

All medications used to treat the subject's CPP in the last 12 months prior to Screening, including all GnRHa medications, will be recorded in the appropriate electronic case report form (eCRF).

Any questions regarding concomitant or prior therapy should be raised to the AbbVie emergency contact (TA MD). Information regarding potential drug interactions with LA is located in the Lupron Depot package insert.

5.4 Withdrawal of Subjects and Discontinuation of Study

Study subjects and/or their parent or legal guardian have the right to prematurely withdraw from the study at any time.

The investigator may discontinue any subject's participation for any reason, including an adverse event, safety concerns, or failure to comply with the protocol.

Subjects will be withdrawn from the study immediately if any one of the following occurs:

- Clinically significant abnormal laboratory results or adverse events, which rule out continuation of study drug, as determined by the Investigator or the AbbVie TA MD.
- The subject requests withdrawal from the study.
- It is in the subject's best medical interest.

- Eligibility criteria violation was noted after the subject started study drug and continuation of study drug would place the subject at risk.
- Introduction of prohibited medications or dosages and continuation of study drug would place the subject at risk.
- An adverse event occurs that the investigator feels is detrimental to the subject.
- The subject requires treatment with another drug that will interfere with evaluation of the investigational product.
- Subject is significantly noncompliant with study procedures, which would put the subject at risk for continued participation in the trial.
- Subject demonstrates severe allergic reaction to the investigational product.
- Subject is pregnant.
- Subject is not adequately suppressed on therapy as evidenced by peak stimulated LH level of ≥ 4 mIU/mL at or after Week 24 **and** subject has an accelerated progression of pubertal symptoms any time after Week 24, specifically > 1 -stage progression in breast or genitalia (not pubic hair) from the last visit as assessed by the same individual, if possible.

For subjects to be considered lost to follow-up, reasonable attempts must be made to obtain information on the subject's final status. At a minimum, 2 phone calls must be made and 1 certified letter must be sent and documented in the subject's source documentation.

AbbVie may terminate this study prematurely, either in its entirety or at any site. The investigator may also stop the study at his/her site if he/she has safety concerns. If AbbVie terminates the study for safety reasons, AbbVie will promptly notify the investigator.

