Part 2: Following completion of Part 1 assessments, subjects will continue to Part 2 of the study (extension period) to evaluate long-term administration of LA 45 mg 6-month (up to 24 months). Study visits during the extension period will start at Week 48 and continue once every 24 weeks for 96 weeks (24 months) until the subject discontinues treatment of LA 45 mg 6-month or withdraws from the study. Subjects will be assessed for continued maintenance of LH suppression and safety throughout this extension period.

Note: Week 48 is the end of Part 1 and also the start of Part 2. See [Appendix D](#) of the protocol and Section 2 of the Operations Manual for details.

Some of the study visits and visit activities (including but not limited to clinical laboratory tests and concomitant medication assessment) may be conducted in a non-hospital/clinic environment (e.g., the subject's home) by qualified individuals at the request of the Investigator and with the agreement of AbbVie, the subject, and subject's parent or legal guardian.

[figure not shown]
If a subject cannot come to the site because of an unforeseen circumstance (e.g., the COVID-19 pandemic), study visits may be conducted virtually by site staff (e.g., by phone or video) or by a qualified home healthcare nurse in a non-hospital/clinic environment (e.g., the subject's home) at the request of the investigator and with the agreement of the subject's parent or legal guardian. AbbVie should be notified if this occurs.

Details of the study procedures are located in the Operations Manual ([Appendix F](#)).

A schematic of the study is shown in [Figure 1](#).

Figure 1. Study Schematic

Children with CPP (N = ~40)

AOC = acute-on-chronic; CPP = central precocious puberty; E2 = estradiol; T = testosterone; FSH = follicle-stimulating hormone; IM = intramuscular; LH = luteinizing hormone; PK/PD = pharmacokinetic/pharmacodynamic

- At the beginning of Part 2, half of the subjects will be randomly selected for AOC biochemical assessments 48 hours after the injection of study drug at Weeks 48, 72, 96, and 120.

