5.5 Follow-Up for Subject Discontinuation of Study Drug or from Study

To minimize missing data, subjects who prematurely discontinue study drug treatment should continue to be followed for all regularly scheduled visits, unless subjects and their parent or legal guardian have decided to discontinue study participation entirely (withdrawal of informed consent). Subjects and their parent or legal guardian should be advised on the continued scientific importance of their data even if they discontinue treatment with study drug early.

If a subject prematurely discontinues study participation (withdrawal of informed consent), the procedures outlined for the Premature Discontinuation visit should be completed as soon as possible, preferably within 2 weeks. In addition, if the subject and parent or legal guardian is willing, a 12-week follow-up phone call after the last visit may be completed to ensure all treatment-emergent adverse events/serious adverse event (SAE) have been resolved.

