At Week 24 (and Weeks 48, 72, 96, and 120 for subjects who continue to Part 2), the LA 45 mg study drug injection must be administered after the last blood collection (60 minutes) for the stimulation test. If the Week 24 (and Weeks 48, 72, 96, and 120 for subjects who continue to Part 2) stimulation test results indicate inadequate peak LH suppression (≥ 4 mIU/mL), the subject may be asked to return to the clinic to be evaluated for signs/symptoms of puberty progression. If this occurs, the visit will be documented as an unscheduled visit. Unscheduled blood samples for basal or stimulated LH, FSH, testosterone (in male subjects), or estradiol (in female subjects) may be collected according to the investigator's clinical judgment at any time throughout the study and sent to the central laboratory for analysis and resulting.

If a subject cannot come to the site because of unforeseen circumstances (e.g., the COVID-19 pandemic), the GnRHa stimulation test and required gonadotropins and sex steroids blood samples collection may be performed by a home healthcare nurse at the subject's home. AbbVie should be notified if this occurs. Refer to the Laboratory Manual for sample collection instructions.

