3.27 Subject Withdrawal from Study

All attempts must be made to determine the date of the last study drug dose and the primary reason for discontinuation of study drug or study participation. The information will be recorded on the appropriate eCRF page; however, these procedures should not interfere with the initiation of any new treatments or therapeutic modalities that the investigator feels are necessary to treat the subject's condition. Following discontinuation of study drug, the subject will be treated in accordance with the investigator's best clinical judgment, irrespective of whether the subject or the subject's parent or legal guardian decides to continue participation in the study.

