6 STUDY DRUG

6.1 Treatments Administered

Study drug (LA 45 mg 6-month) will be administered at the visits listed in Section 2. LA 45 mg 6-month drug product will be injected intramuscularly once every 24 weeks. Each injection should be administered in a different anatomical site to minimize injection site reactions.

LA 45 mg 6-month drug product will be provided by AbbVie as a pre-filled dual chamber syringe containing sterile lyophilized microspheres, which when mixed with diluent, become a suspension

intended for intramuscular injections to be given once every 24 weeks. The front chamber of the LA formulation pre-filled dual chamber syringe contains LA (45 mg), and the second chamber contains diluent. Study drug must be prepared as described in the instructions for drug preparation (refer to Section 7.3).

Study drug must not be administered without contacting the IRT system. Study drug may only be administered to subjects enrolled in the study through the IRT system. If a subject cannot come to the site because of unforeseen circumstances (e.g., the COVID-19 pandemic), the site may contact the IRT for kit assignment. Study drug can then be dispensed as described in Section 3.19.

At the end of the Treatment Period or at the Premature Discontinuation Visit, the site will contact the IRT system to provide visit date information.

The GnRHa stimulation test will be conducted using generic LA aqueous solution. For the stimulation test, 20 µg/kg of generic LA aqueous solution will be administered subcutaneously. Generic LA aqueous solution will be supplied to the sites for the purpose of conducting the stimulation test. Each site will be responsible for maintaining drug accountability records, including product description, manufacturer, lot numbers, and administration to subjects. Sites should use their standard of care practice for preparation of the injection site and injection of generic LA aqueous solution. If a subject cannot come to the site because of unforeseen circumstances (e.g., the COVID-19 pandemic), the GnRHa stimulation test may be performed by a home healthcare nurse at the subject's home.

There may be times when the sponsor is unable to provide the generic LA aqueous solution. Under these circumstances, the participating sites have the option to obtain this product through an external licensed pharmacy or wholesaler or from local site supplies.

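### Protocol 5.4 and 4.1 end visits for events that need only stop the drug, 5.5 keeps those children in, and no text says which prevails, so Tanner, growth and bone-age data can be lost because of the outcome

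*Protocol*

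**What the plan says.** Four places govern what happens when a child stops study drug.

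- **Protocol 5.4**: "Subjects will be withdrawn from the study immediately if any one of the following occurs". Several listed events are, by their own wording, reasons to stop the drug: laboratory results or adverse events that rule it out, eligibility or prohibited-medication problems where more drug would be a risk, severe allergic reaction, and inadequate LH suppression at or after Week 24 combined with breast or genital progression of more than one stage.
- **Protocol 4.1**, repeated in SAP 4.2.1: Part 2 visits run every 24 weeks "until the subject discontinues treatment of LA 45 mg 6-month or withdraws from the study". Stopping treatment is enough to end them.
- **Protocol 5.5**: to limit missing data, "subjects who prematurely discontinue study drug treatment should continue to be followed for all regularly scheduled visits". Its one exception is withdrawal of informed consent.
- **Operations Manual 3.27** (Protocol Appendix F): after drug is stopped the child is treated on clinical judgment, "irrespective of whether the subject or the subject's parent or legal guardian decides to continue participation in the study". This assumes that a child off drug may stay in the study.

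On analysis, SAP 4.9 summarises data as observed unless stated otherwise. Missing stimulated LH counts as failure (SAP 4.9 for Part 1, SAP 8.1 for any scheduled visit). SAP 8.3 removes a child from the sex-steroid denominator after a missed injection.

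**The concern.** A 5.4 event is not a withdrawal of consent, so 5.4 and 5.5 give opposite instructions for the same child. The Part 2 sentence in 4.1 contradicts 5.5 for every drug stop in Part 2, listed or not. With about 20 sites and 40 children, practice could differ between sites.

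One of the 5.4 criteria is itself a poor outcome: LH failure with rapid pubertal progression. If those children leave, the later Tanner, growth and bone-age summaries describe the children who remain, and the worst responders are missing for a reason tied to what is being measured. Unlike stimulated LH, these endpoints have no rule that counts a missing value as failure.

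**Working it through.** **The texts applied to one child.** Suppose the Week 24 stimulation test shows peak LH of 4 mIU/mL or more. Under Operations Manual 3.15, "the subject may be asked to return to the clinic to be evaluated for signs/symptoms of puberty progression". If staging at that unscheduled visit shows progression of more than one stage:

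- Protocol 5.4 takes the child out of the study at once.
- Protocol 4.1 and SAP 4.2.1 give no Part 2 visits, because treatment has stopped.
- Protocol 5.5 keeps the child in all remaining visits.
- Operations Manual 3.27 leaves participation to the family.

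No sentence in the protocol, Operations Manual or SAP ranks these rules.

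**Assessments lost.** Protocol Appendix D and Operations Manual 2 schedule Tanner staging and bone age after baseline at Weeks 24, 48, 72, 96, 120 and 144, which is 6 visits. Share lost = scheduled visits after exit / 6.

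| Exit | Visits lost | Share |
|---|---|---|
| Before Week 24 | 6 of 6 | 100% |
| Between Weeks 24 and 48 | 5 of 6 | 83% |
| At the Week 48 visit | 4 of 6 | 67% |
| At the Week 72 visit | 3 of 6 | 50% |
| At the Week 96 visit | 2 of 6 | 33% |

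Height is measured at 10 post-baseline visits (Weeks 4, 12, 20, 24, 44, 48, 72, 96, 120, 144). Exit between Weeks 24 and 44 loses 6 of 10, and exit at Week 72 loses 3 of 10. A Premature Discontinuation visit can return one off-schedule assessment of each kind. Losses from Week 72 onward follow from 4.1 as well as from 5.4.

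**Which endpoints are exposed.**

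- *Stimulated LH*: a withdrawn child is a failure at each later visit (SAP 4.9, 8.1), and SAP 8.3 keeps every child dosed on Day 1 in the denominator. The rate is not inflated by withdrawal.
- *Sex steroids*: once an injection is missed, SAP 8.3 excludes the child whether retained or withdrawn, so later percentages do not depend on which rule a site follows. Only values within a dosing interval already begun can be lost, for example Weeks 12 to 24 after the Day 1 dose.
- *Tanner, growth, bone age*: as observed, with no protection.
- *Primary endpoint*: the LH-plus-progression criterion cannot operate before Week 24, so only non-efficacy withdrawals before Week 24 matter. The test precedes the second dose, so such a child could still be tested under 5.5, but under 5.4 becomes a failure. Each one who would have tested suppressed lowers the rate by 1/40 = 2.5 points.

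The plan gives no figure for this point. Its precision figure of 16.7% at N = 40 (Protocol 7.3, SAP 4.4) does reproduce: the largest distance from x/40 to an exact 95% limit is 0.1670. Nothing here depends on it.

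**The case against.** The best defence is that 5.4 is a specific, mandatory list and 5.5 is general and advisory, so 5.4 governs its list and 5.5 governs the rest. A site could work that way, and a child who stops for an unlisted reason in Part 1 meets no conflict. But 5.5 names consent withdrawal as its only exception, and this reading leaves 4.1 unexplained, because 4.1 ends Part 2 visits for every drug stop. That 4.1 is a design overview softens it, but the SAP repeats it.

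It can also be said that retention alone does not repair the Tanner table. A retained child may be suppressed on another GnRHa and then be counted as a success. That stands, and is why the fix needs an SAP rule as well as protocol wording.

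Three stronger readings are tempting, and the documents do not support them.

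- *The primary result is at risk.* With assumed counts, 36/40 (90.0%) has an exact 95% interval of 76.3% to 97.2%, and 35/40 (87.5%) has 73.2% to 95.8%. The lower limits fall either side of the 75% in SAP 4.3.1. But SAP 4.8 says no hypothesis is tested, no success rule is attached to 75%, and the direction is conservative. Children with severe allergy to leuprolide, pregnancy or another GnRHa would remain failures under the fix too.
- *The Tanner bias has a known size.* If k of n children would count as unsuppressed and a share p of the rest is suppressed, the as-observed table overstates by p - p(n - k)/n = pk/n. At an assumed p = 0.9 and n = 40, k = 1, 2 and 4 give 2.25, 4.5 and 9.0 points. The documents give neither p nor k. The criterion also needs LH failure and progression of more than one stage together, so one-stage progressors and progressors with suppressed LH are not caught by it.
- *Safety follow-up is lost.* Protocol 6.1 and Operations Manual 4.1 separately require adverse-event collection to 24 + 12 = 36 weeks after the last dose. Inconsistent practice is possible, but the text does not drop this follow-up.

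**Conclusion.** The contradiction is real and should be resolved. Its cost falls on Tanner, growth and bone-age summaries. A child who leaves between Weeks 24 and 48 loses 5 of 6 scheduled Tanner and bone-age assessments, and one who leaves at Week 72 loses 3 of 6, less one discontinuation assessment. One route out is the outcome itself. The per-child counts come from the visit schedule. How many children are affected is not stated, so no overall bias is claimed, and the loss arises only where a site follows 5.4 or 4.1 in preference to 5.5. Stimulated LH and later sex-steroid percentages are protected by SAP rules. The effect on the primary endpoint is limited to non-efficacy withdrawals before Week 24, is conservative at 2.5 points per child who would have tested suppressed, and has no formal test at stake.

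**What to change.** Leave the criteria for stopping treatment as they are, and change what follows from them.

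1. **Protocol 5.4**: reword the lead-in so that the drug-related events lead to discontinuation of study drug with 5.5 follow-up. Reserve study withdrawal for withdrawn consent or where participation itself is unsafe. Limit pregnant subjects to safety follow-up. Omit the stimulation test after severe allergy to leuprolide, because the test injects it (Operations Manual 6.1: "The GnRHa stimulation test will be conducted using generic LA aqueous solution").
2. **Protocol 4.1 and SAP 4.2.1**: align the Part 2 visit sentence with 5.5.
3. **SAP**: count children who stop for LH failure plus progression as failures in later Tanner summaries, flag data after another GnRHa starts, and do not score LH suppression after that point as study-drug success.

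Two clarifications are optional. Protocol 5.5 describes the Premature Discontinuation visit only for withdrawn consent, although the visit schedules list it without that condition. The Protocol 5.2 medicines that "will not be permitted for use during the study" and the 5.4 criterion "The subject requires treatment with another drug that will interfere with evaluation of the investigational product" could be limited to time on study drug, to match Operations Manual 3.27.

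The cost is a few sentences of wording and one set of SAP rules. No visit is added beyond those 5.5 already asks for, and Protocol 5.3 already records concomitant medication. The downside is a real one in children: those off drug keep the stimulation tests with serial blood draws, radiographs and, in girls, pelvic ultrasound. Families may decline, and some off-drug data will need flagging.
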